### Potential benefits of the study

Pouchitis affects a considerable amount of patients after IPAA surgery, and can result in either loss of anal defecation due to removal of the pouch and creation of a permanent ileostomy, or in certain centers the construction of a new pouch. Both are associated with risks of additional surgeries for the patient. In addition, the current treatment with oral metronidazole can result in serious side effects due to repeated, high doses, and it is important to determine whether an alternative or lower dosage can be as effective. We hypothesize that GM-CSF with Fosfomycin and metronidazole will have an effect on the PDAI and bacterial dysbiosis, and potentially give rise to fewer side effects than conventional medical therapy because of local instead of systemic application.

### Potential risks of the study

The risk of endoscopy of the pouch (pouchoscopy) will be relatively low, compared to colonoscopy, and includes bleeding, perforation, infection and adverse reaction to sedatives and analgesia given. There are no data on perforation risk of pouchoscopy, but in colonoscopy overall, the pooled prevalence is described as 0.5/1000 (95% CI 0.4-0.7), including both diagnostic and interventional colonoscopy. Bleeding rate for colonoscopy occurs in 2.6/1000 (95% CI 1.7-3.7) and mortality at 2,9/100,000 (95% CI 1.1-5.5).

Because endoscopy of the pouch is not technically complicated and only takes a short time, most patients will not require sedation or analgesia, but is possible, depending on the patient's wishes. The endoscopy of the pouch will be performed by a trained specialist surgeon in the outpatient endoscopy clinic.

### GM-CSF

Knowledge about adverse reactions after GM-CSF is mainly based on i.v. (intravenous), i.m. (intramuscular) and s.c. (subcutaneous) administration. We suspect that application of a low dose of 50 µg to the mucosa of the pouch will result in less frequent systemic adverse reactions.

Fever is the most common adverse effect, often accompanied by myalgia and malaise, and occurs in more than 20% of recipients of the conventional systemic dose of 250 µg. For GM-CSF application, the following known and usual side effects (1-10%) and known and non-usual side effects (0.1-1%) will not be registered as adverse reactions: fever, malaise, myalgia, abdominal pain, diarrhea, rash, chest pain, weight loss, nausea and vomiting, peripheral edema, dyspnea, hypoxemia, hypotension, tachycardia, flushing, metabolic disease, hyperbilirubinemia, cardiac dysrhythmia and pharyngitis (65).

Effects are more common when GM-CSF is administered intravenously and with doses greater than 3 µg/kg. High doses (20 µg/kg/day) of GM-CSF have been reported to cause a generalized capillary leak syndrome (4,66). In our study, only 50 µg are applied locally in the pouch.

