## 1. Summary

A definitive cure for patients with treatment-refractory ulcerative colitis is proctocolectomy with IPAA (restorative ileal pouch anal anastomosis) (1). Up to 50% of all patients develop “pouchitis” within the first five years after surgery, an inflammatory condition that is as yet poorly understood and without official consensus on treatment (2). Treatment modalities include oral antibiotics as well as immunomodulators, steroids, probiotics and biological agents, but up to 20% of these patients develop chronic, treatment-resistant pouchitis, which can result in pouch failure and the need for reoperation with the possible creation of an ileostomy (11,12).

The etiology of pouchitis is thought to be similar to other inflammatory bowel diseases, in that genetic and bacterial factors, a compromised gastrointestinal barrier and immunological components seem to play a role. Its pathogenetic mechanisms seem to mimic Crohn’s disease, in which smaller studies have shown some effect of systemically administered GM-CSF (granulocyte-macrophage colony stimulating factor) on the gut macrophage function in clearing microorganisms and maintaining the mucosal barrier (3–6).

We hypothesize that GM-CSF will have an effect in the treatment of pouchitis because of its similarity to that of Crohn’s disease. In order to maximize effect on the inflamed mucosa and minimize systemic side effects, we intend to administer it locally in the pouch. In a safety and proof-of-concept intervention study we will combine 50 µg GM-CSF with two well-known antibiotics, 400 mg Fosfomycin and 100 mg metronidazole, to target both the suspected immunological as well as the bacterial role in the pathogenesis of pouchitis.

The effect on the pouch will be assessed endoscopically and histologically by taking biopsies that will also be examined for changes in the microbiome. Patients will be clinically examined and have blood samples taken to monitor for adverse reactions. The primary outcome measure will be an assessment of adverse reactions and tolerability of the drug. Secondary outcome measures will be a change in the pouchitis disease activity index (PDAI), a change in the microbial diversity, and a change in inflammatory markers.

This study is based on a non-randomized trial design with an open-label single group assignment.

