#### Phase I – Safety study

##### Primary outcome measure

- Safety: Determine serious adverse reactions or adverse reactions from the application of GM-CSF, metronidazole and fosfomycin in the pouch as seen in Appendix 8. The category of the reactions will be determined by the principal investigator according to the safety assessment described in chapter 7.  
A summary of the product characteristics of GM-CSF, fosfomycin and metronidazole will function as a reference document in evaluation of adverse effects. We will monitor adverse reactions from the day of the intervention in Phase I and II until respectively day 30 and 37. The safety of the intervention will be measured by adverse reactions.

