### Secondary outcome measures

- Change in the clinical, endoscopic or histological PDAI – A decrease of 3 points or more will be determined as an improvement in PDAI from before application of the study drug to 7 days after application of the study drug
- Change in median WBC, CRP, creatinine and liver enzymes from before application of the study drug to 7 days after application of the study drug
- Change in microbial diversity in the pouch using 16S rRNA sequencing from before application of the study drug to 7 days after application of the study drug
- Safety: Determine serious adverse reactions or adverse reactions from the application of GM-CSF, metronidazole and fosfomycin in the pouch as seen in Appendix 8.

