### **Metronidazole**

Treatment with metronidazole is known to create Antabuse-like reactions in patients who continue to drink alcohol. Patients who are currently heavy drinkers are excluded from study participation. Patients will be orally instructed not to drink alcohol from the day before the therapeutic endoscopy during the enrollment meeting until one week after the last intake of metronidazole.

For metronidazole application, the following known and usual side effects (1-10%) and known and less usual side effects (0.1-1%) will not be registered as adverse reactions: nausea, glossitis, dry mouth, dysgeusia, stomatitis, myalgia, superinfection with candida, dark coloration of the urine.

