### **Fosfomycin**

Based on the literature on the effects of fosfomycin, the following known and usual side effects (1-10%) and known and less usual adverse reactions (0.1-1%) will not be registered as adverse reactions: phlebitis, abdominal pain, decreased appetite, dysgeusia, vertigo, light headache, nausea, vomiting, diarrhea, rash, fatigue (54).

The chief adverse effects of fosfomycin are gastric irritation from orally administered fosfomycin disodium, evidence of allergy in the form of transient rashes (0.3% of cases) and eosinophilia (0.2%), as well as transiently raised liver enzymes (0.3% of cases) from systemically administered fosfomycin (62). In general, however, fosfomycin displays remarkably low toxicity, so that when high doses of fosfomycin disodium are given systemically (up to 28 or 32 g per day), it is the sodium load that is the dose-limiting factor (54). It is recommended that the dosage of Fosfomycin is lowered in patients with a GFR < 40 ml/min. Our study only administrates 400 mg Fosfomycin daily, substantially lower than normal doses of Fosfomycin (8-12 grams daily). Therefore, we do not expect there to be a need for lowering the dosage in patients with renal impairment. For ensuring optimal safety, however, we will exclude patients with an eGFR < 40 ml/min in this study.

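### The protocol bars 31 known drug effects from registration as adverse reactions, against its own definition of an adverse reaction and its Phase I primary outcome

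*Protocol*

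**What the plan says.** The summary states: "The primary outcome measure will be an assessment of adverse reactions and tolerability of the drug". In section 3, the Phase I primary outcome says that "The safety of the intervention will be measured by adverse reactions", and the Phase II secondary outcomes repeat the task: "Determine serious adverse reactions or adverse reactions from the application of GM-CSF, metronidazole and fosfomycin in the pouch as seen in Appendix 8".

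Later in section 3, under the risks of each drug, three parallel clauses remove known effects from that category:

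- GM-CSF: "will not be registered as adverse reactions: fever, malaise, myalgia, abdominal pain, diarrhea, rash, chest pain", with the list ending "tachycardia, flushing, metabolic disease, hyperbilirubinemia, cardiac dysrhythmia and pharyngitis".
- Metronidazole: "will not be registered as adverse reactions: nausea, glossitis, dry mouth, dysgeusia, stomatitis, myalgia", followed by two more effects.
- Fosfomycin: "known and less usual adverse reactions (0.1-1%) will not be registered as adverse reactions: phlebitis, abdominal pain", followed by nine more.

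Section 7, Adverse reactions, makes an adverse event an adverse reaction when the study drug may reasonably have caused it. It makes no exception for effects already known. Section 7, Serious adverse events or reactions, sends all adverse reactions to the medicines agency and the ethics committee in an annual report.

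Appendix 8, the follow-up form, prints the listed effects as tick boxes in a side-effects field. A separate field is headed for adverse reactions.

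**The concern.** Safety in Phase I is measured by one category of event, and two parts of the protocol draw that category differently. Two people with identical data from the same six patients could report different primary results, each citing the protocol. The principal investigator assigns the category in an open-label trial, so the rule should be settled before any data are seen.

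The same events would also be in or out of the annual report of adverse reactions, depending on the section followed. Non-serious reactions are a large part of what a small, single-dose tolerability study sets out to describe.

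**Working it through.** **Step 1. Count the exempted effects** (section 3; nausea and vomiting counted separately).

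- GM-CSF: 20 entries.
- Metronidazole: 8 entries. Nausea and myalgia are already on the GM-CSF list, so 6 are new.
- Fosfomycin: 11 entries. Abdominal pain, nausea, vomiting, diarrhea, rash and dysgeusia are already listed, so 5 are new.
- Entries: 20 + 8 + 11 = 39. Distinct effects: 20 + 6 + 5 = 31.

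**Step 2. Follow one event through the text.** Take a new, mild, non-serious fever after dosing that the investigator judges related.

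- Section 7, Safety assessments: it is an adverse event and is captured with onset, severity, relationship and resolution.
- Section 7, Adverse reactions: it is related, so by definition it is an adverse reaction.
- Section 3, GM-CSF: it is not registered as an adverse reaction.
- Section 3, Phase I primary outcome: it adds 1 under section 7 and 0 under the GM-CSF clause.
- Section 7, annual report: included under the definition, left out under the clause.
- Appendix 8: it is ticked as a side effect. The outcome's reference to Appendix 8 could mean the whole form, in which case it counts, or only the adverse-reactions field, in which case it does not.

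No reading satisfies both the section 3 clause and the section 7 definition.

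**Step 3. Direction.** The clauses only remove events and never add any. Following them gives a count equal to or lower than the section 7 count.

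**Step 4. Scale.** If the result is summarised as the share of patients with at least one adverse reaction, a patient whose only reaction is a listed one moves it by 1/6 = 16.7 percentage points in Phase I and 1/12 = 8.3 in Phase II. How many such patients to expect cannot be worked out. The protocol gives no rates for use in the pouch, says that knowledge of GM-CSF reactions comes mainly from injected use, and expects fewer systemic reactions locally.

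**Step 5. What is outside the conflict.**

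- Serious events: section 7 treats all of them as related and reports them as SUSARs.
- The Phase II criterion in section 4 that no serious events occurred is unaffected. However, section 4 also calls for an assessment of safety, and section 10 starts Phase II only if the risk and safety results are favourable. That wider judgement could be influenced by a lower count.

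**The case against.** The strongest reply is that nothing is lost. Section 7 captures every adverse event with severity and relationship, patients are asked about the listed effects, and Appendix 8 ticks them. Anyone could recover the related events at analysis. The summary's primary outcome also includes tolerability, which the clauses do not restrict. This stands, and it makes the defect one of classification. It does not cure it, because the Phase I outcome names adverse reactions as the measure, and Appendix 8 keeps them apart from side effects.

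It may also be said that the lists only mark what is expected. They do not say so: they bar registration. Sections 3 and 7 already give the reference role to the product characteristics, with section 7 adding the investigator's brochure. Section 7 does use permissive wording when it says how a related event may be classified, but the definition that opens the subsection is unconditional.

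Some stronger readings are tempting and are not supported:

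- *The count is biased downward.* Only if the section 3 clauses are the ones followed.
- *Safety oversight fails.* Section 8 allows a halt on any suspicion about patient safety, and section 5 covers withdrawal for adverse events and laboratory abnormalities as well as reactions. Neither rests on the adverse-reaction label alone.
- *Measuring bilirubin while exempting hyperbilirubinemia is a contradiction.* A routine blood panel does not conflict with a rule about labels.
- *The fosfomycin clause contradicts itself* by calling part of its list adverse reactions. The parallel clauses say side effects, so this looks like a wording slip.
- *Fever is misclassified.* The protocol says fever "occurs in more than 20% of recipients of the conventional systemic dose" and then lists it under bands of 1-10% and 0.1-1%. The bands carry no dose or route, so this is unclear rather than plainly wrong.

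**Conclusion.** The contradiction is real and needs correcting. The section 3 clauses, covering 31 distinct effects, cannot be reconciled with the section 7 definition, with the Phase I primary outcome and its Phase II secondary counterpart, or with the annual reporting of all adverse reactions.

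The consequence is conditional. Under the section 3 clauses, related non-serious listed events leave the adverse-reaction count and the annual report. Under the section 7 definition, or if the outcome refers to all of Appendix 8, they stay in. The direction is certain once the clauses are applied; the amount is not derivable from the protocol.

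The conclusion assumes that some listed events will be non-serious and judged related. Not every tick will qualify: fever and abdominal cramps are also items of the disease activity index, and a condition present at baseline is not an adverse event unless it worsens.

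**What to change.** 1. In section 3, delete the three non-registration clauses. Alternatively, restate the lists as serving only to judge whether a non-serious event is expected, leaving section 7's handling of serious events as it is.
2. In the Phase I primary and Phase II secondary outcomes, state that every event judged related under section 7 counts, including a ticked Appendix 8 item or a laboratory finding. Show expected and unexpected reactions separately.
3. Add a line to Appendix 8 linking each ticked item to the adverse-event form, so that relationship is assessed for it.
4. Minor: say which dose and route the GM-CSF frequency bands refer to, and reconcile them with the figure given for fever.

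The cost is protocol wording and one line on a form, with no extra visits or tests. The reported reaction rate may look less favourable.

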### **Metronidazole**

Treatment with metronidazole is known to create Antabuse-like reactions in patients who continue to drink alcohol. Patients who are currently heavy drinkers are excluded from study participation. Patients will be orally instructed not to drink alcohol from the day before the therapeutic endoscopy during the enrollment meeting until one week after the last intake of metronidazole.

For metronidazole application, the following known and usual side effects (1-10%) and known and less usual side effects (0.1-1%) will not be registered as adverse reactions: nausea, glossitis, dry mouth, dysgeusia, stomatitis, myalgia, superinfection with candida, dark coloration of the urine.

### **Fosfomycin**

Based on the literature on the effects of fosfomycin, the following known and usual side effects (1-10%) and known and less usual adverse reactions (0.1-1%) will not be registered as adverse reactions: phlebitis, abdominal pain, decreased appetite, dysgeusia, vertigo, light headache, nausea, vomiting, diarrhea, rash, fatigue (54).

The chief adverse effects of fosfomycin are gastric irritation from orally administered fosfomycin disodium, evidence of allergy in the form of transient rashes (0.3% of cases) and eosinophilia (0.2%), as well as transiently raised liver enzymes (0.3% of cases) from systemically administered fosfomycin (62). In general, however, fosfomycin displays remarkably low toxicity, so that when high doses of fosfomycin disodium are given systemically (up to 28 or 32 g per day), it is the sodium load that is the dose-limiting factor (54). It is recommended that the dosage of Fosfomycin is lowered in patients with a GFR < 40 ml/min. Our study only administrates 400 mg Fosfomycin daily, substantially lower than normal doses of Fosfomycin (8-12 grams daily). Therefore, we do not expect there to be a need for lowering the dosage in patients with renal impairment. For ensuring optimal safety, however, we will exclude patients with an eGFR < 40 ml/min in this study.

### **Drug combination risks**

One recent study tested intraperitoneal administration of GM-CSF for peritonitis on patients undergoing laparoscopic appendectomy for uncomplicated appendicitis in 14 otherwise healthy male individuals. In this Phase II trial, 50 µg of molgramostim was administered into the peritoneal cavity directly after appendectomy, along with 4 g of fosfomycin and 1 g of metronidazole.

No serious adverse events or complications occurred. Adverse events included dizziness, diarrhea, hypotension, no flatus and discomfort when breathing deeply. However, it was not possible to determine if these occurred due to the study drug combination, or were complications related to the anesthesia,

surgery or appendicitis. It is also unclear if these adverse events, if related to the study drug, were a reaction to the GM-CSF, fosfomycin or metronidazole (67).

We hypothesize therefore, that application of the study drug combination is safe in the pouch. We will also be using a lower dosage of fosfomycin and metronidazole.

### **Bias**

This study is an open-label proof-of-concept study with a single treatment arm. There is no blinding of patients or the investigator. The only blinded examination is the pathology examination of mucosal biopsies of the pouch and 16S rRNA sequencing. The pathologist is unaware of whether samples are taken before the application of the study drug or after. Therefore, the histology of the PDAI should not be influenced by bias.

## **4. Study design**

This study is a clinical proof-of-concept intervention study. It is based on a non-randomized trial design with an open-label single group assignment. See chapter 7 for a flow chart of the trial phases and study visits.

### Phase I

Tolerability of the treatment is tested on 6 patients with a single dose of the combined medication applied endoscopically. See also appendix 14 for a flow-chart.

Patients will be identified by the treating gastroenterologist through the outpatient clinic when presenting with pouchitis and then informed in detail and screened according to the inclusion and exclusion criteria. The patient then gets at least 24 hours to reflect before signing the informed consent form to enter the trial.

- Day 1:
  - Clinical examination is performed and pre-treatment blood samples taken
  - Endoscopy with biopsies is performed and GM-CSF, metronidazole and fosfomycin is sprayed into the pouch as a single dose
- Day 7:
  - Clinical examination, post-treatment blood samples,
  - Endoscopy with biopsies
  - Recording of any adverse reactions or other adverse events (can be any day between day 6-9)
- Afterwards, the patient receives the standard treatment at Zealand University Hospital for acute pouchitis, consisting of a 10-day course of oral metronidazole 500 mg x 3 or ciprofloxacin 500 mg x 2.
- Day 30:
  - Telephone call to the patient to ask about symptoms of pouchitis and any side effects. (Can be any day between day 30 and 37).

After the last patient in phase I has had their 30 day follow-up, the safety and feasibility of the study drug application will be assessed by the sponsor and investigators of the study. If no serious adverse events of reactions occurred, the Phase II study will be initiated.

## Phase II:

Depending on effect of the first study, this phase will comprise the treatment of 12 patients with a daily dose of the combined medication. The study drug will be applied in the hospital, to ensure the correct dosage and concentration. See also appendix 15 for a flow-chart.

Clinical and endoscopic control after 14 days with blood samples and biopsies. Patients who have been a part of the Phase I study, can be included if they fulfill inclusion criteria at time of inclusion for Phase II.

Inclusion will follow the procedures from the Phase I trial. Patients will be identified by the treating gastroenterologist through the outpatient clinic when presenting with pouchitis and then informed in detail and screened according to the inclusion and exclusion criteria. The patient then gets at least 24 hours of reflection time before signing the informed consent form to enter the trial.

- Day 1:
  - Clinical examination, blood samples
  - Endoscopy with biopsies and GM-CSF, fosfomycin and metronidazole applied in the pouch as a spray
- Day 2-7:
  - Enema with GM-CSF and metronidazole/fosfomycin applied in the hospital once daily
- Day 14:
  - Clinical examination, blood samples
  - Endoscopy with biopsies
  - Recording of any adverse reactions or other adverse events (Can be any day between day 13-16)
- Afterwards, the patient gets the standard treatment at Zealand University Hospital for acute pouchitis, which consisting of oral metronidazole 500 mg x 3 for 10 days or ciprofloxacin 500 mg x 2 for 10 days.
- Day 37:
  - Telephone call to the patient to ask for symptoms of pouchitis, any side effects. (Can be any day between day 37 and 44).

